Fluoxetine and its metabolite cross the placenta and are also present in breast milk. The effect of fluoxetine on an embryo or fetus, or on a breastfeeding infant, can be harmful. Due to these risks, individuals cannot take part in this study if they are pregnant, trying to become pregnant or breastfeeding. If a potential female participant is of childbearing age, a urine pregnancy test will be obtained at Screen, and a positive result will exclude them from study participation. Potential participants who are sexually active or able to become pregnant will be required to agree to use an approved birth control method for the entire study and for at least two weeks after the last dose of study drug. Acceptable birth control methods for use in this study are abstinence, condoms, or birth control pills.

Suicide Risk

Suicidality will be assessed at each visit by directly asking the subject (when verbal skills are sufficient) and caregiver about any thoughts or behaviors that directly or indirectly might indicate suicidality (e.g., morbid thoughts, self-injury, statements about life not being worth living). The baseline C-SSRS for any subject who endorses suicidality will be done per the instructions at www.cssrs.columbia.edu/clinical_trials.html. The C-SSRS will also be administered at each subsequent visit following the first report of suicidality. If the subject answers "Yes" to Question 4 or 5 on the C-SSRS, the study physician will be notified immediately, and the subject will be emergently evaluated by a licensed study clinician for appropriate assessment and triage. Subjects who develop significant suicidal ideation (plan, gesture, attempt) will be treated and removed from the study if indicated.

Health Assessments, Behavioral Assessments and Checklists

The data in the study are collected for research purposes, but steps will be taken to minimize any risks and discomforts for participants and families. The content of the clinical measures are not deeply personal in nature and are clearly most relevant to the participant's diagnosis, overall functioning and behavior. To minimize the risk of psychological stress that could result from administration of questionnaires and to allow for more flexibility in time, families will be allowed to complete measures at more than one visit or remotely by phone/videoconference if necessary. Stress during administration of assessments to participants will be minimized by promoting awareness among investigators and coordinators of the signs that a participant may need a break and allowing them to take one.

Loss of Confidentiality

Efforts will be made to avoid loss of confidentiality such that the subject's protected health information will not be shared with other people outside of the research study. All records with identifying information will be kept in a secure (locked, non-public) area located at the Lurie Center.

To minimize the risk of loss of confidentiality, participant protected health information will not be shared with anyone not involved in the research study. Subjects' names and specific individual identifying information will not be disclosed in published reports, although this information may be reviewed by the sponsor and/or its representatives and regulatory agencies for the purposes of verifying clinical trial procedures and or data. Records containing identifying information will be stored in a locked area at the Lurie Center or MGB approved online drive, such as REDCap, to which only approved study staff will have access.

8. Benefits

The subject will benefit from a comprehensive medical and psychiatric evaluation. In addition, the subject will receive close monitoring through clinic visits for the duration of the study. Subjects will have the opportunity to receive drug treatment with the potential to be effective for their disorder.

Down syndrome is a chronic severe illness and depression is a common co-morbidity that affects the well-being of the patient and his/her family. Research is necessary to further understand how best to treat depression in DS including the development of tolerated and effective pharmacologic interventions.

9. Statistical Analysis

Sample Size Considerations:

A meta-analysis investigating the effectiveness of fluoxetine treatment estimated the intent-to-treat probability of response to treatment as measured using the CGI-I to be 44% [32]. In addition, the lower bound of the 95% confidence interval for response to treatment from our retrospective study excluded values less than or equal to 50%. A sample size of 20 provides a greater than 90% chance of observing a response rate of 35% or greater if the population probability of response is 44% or greater and a greater than 90% chance of observing a response rate less than 35% if the true probability of response is 20% or less. For safety outcomes, if there is a serious or severe adverse event associated with fluoxetine treatment in the population of adults with DS that occurs with a frequency of 10% or greater, we will have an 85% or greater chance of observing it in the study and concluding there are safety concerns with fluoxetine use for depression in adults with DS, assuming at least 90% (n=18) of participants remain in the study long enough to experience the event. For tolerability, assuming at least 85% of patients complete treatment or withdraw due to adverse effects, a sample size of 20 provides greater than 90% chance of observing a dropout rate due to side effects less than 36%, assuming at least 80% of adults with DS and depression in the population can tolerate a 16 week treatment course, and at least an 80% chance of observing a dropout rate due to side effects of 36% or greater assuming no more than 50% of adults with DS can tolerate a 16 week treatment course. Assuming an overall completion rate of 70%, a sample size of 20 also allows estimation of mean changes in depression scale score and mean dosage at study completion with a 95% confidence interval half width of 0.6 standard deviations, assuming a correlation of 0.5 between baseline and week 16 measurements.

Statistical Analysis Plan:

We will estimate percentage response to fluoxetine treatment, and corresponding 95% confidence interval, for adults with DS using the proportion of participants with CGI-I scores ≤ 2 at 16 weeks. Participants with missing 16-week CGI-I scores will be treated as non-responders. Frequency of all side effects and adverse events and corresponding 95% confidence intervals will be tabulated. Percent tolerating treatment and corresponding 95% confidence intervals will be estimated using the proportion of participants who did not withdraw from the study before 16 weeks due to reasons other than side effects or an adverse event who discontinue treatment due to side effects or an adverse event. We will also use the 16-week study retention rate and corresponding 95% confidence interval, calculated as the proportion of the participants enrolling in the study who remain in the study for 16 weeks, as a measure of feasibility.

To estimate changes in depression scale scores, including the MADRS, HAM-D, GDS-LD, and GDS-CS, we will use repeated measures linear regression models, as implemented in PROC MIXED in SAS and fit using REML estimation, with repeated measurements of clinical scores as outcomes and time, in categories, as the predictor. We will allow unstructured covariance between repeated measurements from the same participant. Our primary interest will be only in the difference between baseline and week 16 scores, but all observed scores will be included as outcomes, given that partially observed scores may be informative for estimation. We will obtain an estimate of 16-week change and corresponding 95% confidence interval using a contrast of the week 16 and baseline model parameters. Sensitivity to change will be compared between scales using standardized effect sizes, calculated using the model-estimated 16-week change in each outcome divided by 1) the model-estimated standard deviation of the outcome at baseline and 2) the model-estimated standard deviation of the change score. Spearman correlations will quantify the strength of association between change in depression scale score and CGI-I ratings among those with observed 16-week data. We will also tabulate and compare the percent of item-level missing data for each scale.

Mean dosage and 95% confidence interval will be calculated among those who complete 16 weeks of treatment. Minimum, median, and maximum dosage will also be reported. Confidence intervals for binomial proportions will be calculated using Wilson's method. All confidence intervals will be two-sided.

10. Monitoring and Quality Assurance

Data Monitoring

The substantial effort and resources that will be devoted to collecting data in this project will be matched by an equally substantial commitment of effort and resources to edit, verify, correct, update, and assemble the resulting data files. Our data management system incorporates quality control at every juncture from data collection through analysis. We have found that this bottom-up approach to data quality is essential, since there is no single procedure that will verify and correct erroneous data. The PI and research assistant are responsible for data collection and accuracy of record keeping and the researchers will convey an attitude that the data management procedures be treated with unwavering gravity, therefore maintaining a high level of quality for this project.

When a participant is enrolled in the study, they will be assigned a unique identification number that is used to identify all data associated with that person, including hard copy, biological specimens, and computerized data. Unique identifiers will be linked to personal data such as names and addresses only by use of a restricted password, thus assuring confidentiality. Data will be collected on hard-copy forms and then verified by data entry personnel. All of the hard copy research data is kept in locked file cabinets at the Lurie Center. Only the PI and primary research assistants will have access to these files, ensuring security of the hard copy records.

We have taken several steps to ensure the quality of data entry. Once data is obtained, the clinician will review the form to make sure that all required items are completed before giving it to the research coordinator responsible for data entry. Several quality control measures are built into our computerized data management.

The electronic database used to house these data until analyses are needed will be a web-based electronic data capture program created uniquely for this project. The database will be password protected and only certain users will be given access to the web-based program. This will protect the electronic data against any unauthorized persons from entering the dataset and jeopardizing the integrity of the data or engaging in some sort of malicious piracy.

As this project matures into the data analysis stage, data will be queried and exported to statistical software for data analysis.

Safety Monitoring

A physician will monitor adverse effects at each visit. In addition, he or she will review vital signs and laboratory data, as they become available. All of these values are recorded and then reviewed continuously by the PI. All AEs that arise are recorded by a physician. This includes documenting the date of onset, duration, severity, seriousness, and relationship to study medication. Any severe or serious AEs will be reported as soon as possible to the PI. All significant AEs as well as the progress of the study will be reviewed and discussed in detail at the biannual meetings of the Lurie Center Data and Safety Monitoring Board (DSMB). The Lurie Center DSMB includes rotating members of the Lurie Center including pediatricians, pediatric neurologists, child and adolescent psychiatrists specializing in developmental disabilities. All serious or unexpected AEs that are possibly related to drug treatment will be reported to the Partner's IRB within 3 working days from notification of the event. Examples of serious AEs include: death, life-threatening event, inpatient hospitalization, persistent or significant disability/incapacity, congenital anomaly/birth defect, and events that require medical or surgical intervention to prevent death, disability, or hospitalization. An unexpected AE is one that is not described in the protocol. Any serious or unexpected AE that is possibly related to fluoxetine will be reported to the IRB according to the reporting guidelines. Any action resulting in temporary or permanent suspension of the study will also be reported to our IRB.

Adverse events will be documented on the Adverse Effects Review form and Adverse Events Log as described above. All AE data will be captured in the electronic database and reviewed at the biannual DSMB meetings. The DSMB will report to the investigator any AEs occurring at a greater than expected frequency. The Investigator will provide this information to the local IRB and sponsor at the time of annual renewal.

Quality Assurance

The Principal Investigator will obtain IRB approval of the protocol and informed consent. All research personnel assigned to the protocol, including the Principal Investigator(s), Clinical Coordinator(s), and study staff, will be required to complete a computer-based training course on the Protection of Human Research Subjects as required by Partners Institutional Review Board. The Study Coordinator will maintain annual documentation of continuing IRB approval. The Principal Investigator will ensure compliance with regulations related to protection of human subjects, specifically including Title 21 CFR 50, 56, and 312 and Title 45 CFR 46, and ICH Good Clinical Practice.

Protocol adherence will be monitored by the principal investigator. If any protocol changes are needed, the PI with the help of coordinators will submit a modification request to the IRB. Protocol changes will not be implemented prior to IRB approval unless necessary to eliminate apparent immediate hazards to the research subjects. In such a case, the IRB will be promptly informed of the change as outlined in the Partners Human Research Committee.

11. Privacy and Confidentiality

- Study procedures will be conducted in a private setting
- Only data and/or specimens necessary for the conduct of the study will be collected
- Data collected (paper and/or electronic) will be maintained in a secure location with appropriate protections such as password protection, encryption, physical security measures (locked files/areas)
- Specimens collected will be maintained in a secure location with appropriate protections (e.g. locked storage spaces, laboratory areas)
- Data and specimens will only be shared with individuals who are members of the IRB-approved research team or approved for sharing as described in this IRB protocol
- Data and/or specimens requiring transportation from one location or electronic space to another will be transported only in a secure manner (e.g. encrypted files, password protection, using chain-of-custody procedures, etc.)

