Data from this study will lay the foundation for the development of evidence-based guidelines for the treatment of depression in DS which will help increase awareness of this comorbidity and promote systematic screening and treatment. Medication treatment strategies for depression used in the general population likely need to be adapted to be safe, tolerable, and effective for adults with DS. Our clinical experience and pilot data suggest that adults with DS may respond to much lower dosages of fluoxetine than are used in the general population and that higher dosages may be associated with intolerable behavioral side effects such as anxiety or behavioral activation [20]. Data from this proposed study will inform best practices for dosing antidepressants in adults with DS. Finally, no specific depression rating

scales have been developed for or validated in DS. Data from this proposed study will inform which existing rating scales can detect depression in DS and which are sensitive to change with treatment. All the rating scales used in this study are in the public domain and therefore can easily be used in clinical practice. The identification of an appropriate rating scale will allow non-psychiatric specialists such as primary care providers as well as psychiatrists with less experience treating adults with developmental disabilities to screen for depression and monitor treatment effects. Overall, the data from this study is expected to improve the accessibility and quality of treatment for depression in DS, a common comorbidity which affects up to 70% of adults with this syndrome

3. General Description of Study Design

[figure not shown]
We are proposing a 16-week, prospective flexibly-dosed, open-label trial of fluoxetine for the treatment of major depressive disorder (MDD) in adults with DS. Participants will be seen at screen, baseline, and following 4, 8, 12, and 16 weeks of treatment. The duration of the trial will allow us to adjust the dose of fluoxetine over the first 12 weeks and allow for stable dosing during the final 4 weeks of the trial. We may complete visits remotely utilizing secure videoconferencing platforms such as Zoom or by phone, as necessary.

*Accommodations for Out of state patients and virtual visits**

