The same IRB-approved accommodations for out of state patients our group is using in a similar open-label drug trial of buspirone for anxiety in Williams syndrome (Protocol #2021P000376) will be utilized for this study. All participants will be seen for either an in-person or virtual visit for the screen and baseline visits, the primary purpose of which are to establish care and determine the diagnosis and treatment plan. The prescription of fluoxetine will occur at the time of the baseline visit. In accordance with the Mass General Brigham Virtual Visit Procedures (applicable as of April 1, 2021), virtual visits will only be conducted with patients who are located in New England and Florida at the time of the visit and only by attending physicians who are licensed in those states. In accordance with the "FAQs for Mass General Brigham Clinicians: Changes to Procedures for Out of State Virtual Visits" (July 15, 2021) guidelines, the weeks 2, 4, 6, 8, 10, 12, and 16 visits will be conducted as "Customary telephone calls." These visits will consist of brief, logistical conversations with the purpose of communicating with subjects, adjusting prescriptions, and ensuring continuity of care by reviewing adverse effects and concomitant treatments/medications. If at any time during a "Customary telephone call" the study team learns of information concerning for new symptoms that are inconsistent with the diagnosis established during the baseline visit, symptoms that warrant a different treatment plan, or any other reason that in the attending physician's judgment that warrants a medical visit, the subject will be referred for either local clinical care within their state or offered an in-person visit in Massachusetts.

**In person regular and endpoint visits will be offered for all participants who are able to attend and participate in study procedures.*

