Study staff will provide participants with information on how to access the video conferencing platform. Study staff will launch the video conferencing in a private and secure area and ask participants to refrain from taking screenshots, photographs, or recordings of any kind with any electronic equipment. Study staff will remind participants that video/phone meetings are similar to a home visit and that we may learn more about their home and/or the people living with them than during a visit at the hospital. For example, study staff may learn information that must be reported to public health or public safety authorities. The Informed consent describes the legal obligation to report known or suspected child or elder abuse. If study staff make such a report, the public health and safety authorities can use the information as they see fit and may end up sharing it with other government agencies.

4. Subject Selection

Twenty-five adults (18-45 years of age), with a diagnosis of DS exhibiting clinically significant symptoms of MDD on standardized rating scales will be included in this trial. Subjects will be selected to participate in the study based on the following Eligibility Criteria:

Inclusion Criteria

1. **Age 18-45 years.**
2. **Diagnosis of DS** confirmed via genetic testing or a clinical diagnosis made by a clinician with significant experience treating patients with DS.
3. **Diagnosis of major depressive disorder** based on Diagnostic and Statistical Manual of Mental Disorders, Fifth Edition (DSM-5) criteria, confirmed through the Structured Clinical Interview for DSM-5 (SCID-5).
4. **Moderately severe depression as evidenced by a Montgomery-Asberg Depression Rating Scale (MADRS) score of 20 or greater** at Screen and Baseline. A severity score on the MADRS was chosen as an inclusion criterion since it has been demonstrated to be sensitive to change in adults with MDD [27].
5. **A Clinical Global Impression Severity Item score ≥ 4 (moderate)** for depression symptoms at Screen and Baseline.

Exclusion Criteria

1. **Active primary diagnosis of obsessive-compulsive disorder, posttraumatic stress disorder, bipolar disorder, psychosis, or substance use disorder.** These disorders are exclusionary since the primary treatment of these disorders may require acute psychosocial or medication treatments that would confound the assessments used in this study. We will evaluate for these disorders using the corresponding SCID-5 modules.

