Participants will be monitored for possible pregnancy throughout the study. If a participant is of childbearing potential, a urine pregnancy test will be obtained at Screen. A positive result on a urine pregnancy test will then be confirmed via a blood pregnancy test, and a positive result on a blood pregnancy test will exclude them from study participation. We will continue to assess for pregnancy at all monthly clinic visits by asking participants if they are sexually active and if they are using contraception. Participants of childbearing potential who are sexually active and are not using an approved contraception method will be asked to complete a urine pregnancy test. A positive result on a urine pregnancy test will then be confirmed via a blood pregnancy test, and a positive result on a blood pregnancy test will exclude them from study participation.

Adverse events will be collected via a structured side effect rating scale completed with the participant and their primary caregiver. This will include a list of side-effects that have been reported with fluoxetine at a rate greater than 10% including sexual dysfunction, anorexia, diarrhea, nausea, dry mouth, anxiety, drowsiness, headache, insomnia, yawning, asthenia, tremor, and pharyngitis. Each of these side effects plus any additional complaints will be rated at baseline on a 4-point scale by the caregiver as follows: 0 = none; 1 = mild; 2 = moderate; 3 = severe. This scale is similar to that used by the RUPP Autism Network. Suicidality will be assessed at each visit by directly asking the subject (when verbal skills are sufficient) and the caregiver about any thoughts or behaviors that directly or indirectly might indicate suicidality (e.g., morbid thoughts, self-injury, statements about life being not worth living), when indicated by positive responses. At baseline, if suicidality is endorsed, the Columbia-Suicide Severity Rating Scale (C-SSRS) will be administered per the instructions at www.cssrs.columbia/ed/clinical_trials.html. The C-SSRS will also be administered at each subsequent visit following the first report of suicidality. Subjects and caregivers will also have information on how to contact the on-call physician from our practice group who provides coverage 24 hours/day and 365 days/year. Physicians taking call are familiar with research protocols and can contact the principal investigator at any time.

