All adverse events picked up on the rating scale as new will be recorded by the physician. The physician will also ask about any visits to the doctor, new medication use (e.g. OTC cold medicine), or any other complaints, in order to be confident that most adverse events are uncovered. The physician will keep a running log of adverse events that will record the date of onset, date of resolution, seriousness, severity, and relationship to study intervention (e.g., definite, probable, possible, remote, or none) as well as whether the adverse event led to a change in study intervention or other treatment.

A physician will review vital signs as they become available. All significant adverse events as well as the progress of the study will be reviewed and discussed in detail at the biannual meetings of the Lurie Center Data and Safety Monitoring Board (DSMB). The DSMB includes rotating members of the Lurie Center including pediatricians, pediatric and adult neurologists, pediatric and adult psychiatrists, and independent members outside the Lurie Center.

If at any time during the course of the study, the DSMB judges that the risk to subjects outweighs the potential benefits, the DSMB shall have the discretion and responsibility to recommend that the study be terminated.

Schedule of Measures:

Table 1. Schedule of Measures		Treatment Phase
-------------------------------	--	-----------------

Mass General Brigham Institutional Review Board
Intervention/Interaction Detailed Protocol

Measure	#Screen ^^	#Baseline ^^^	Week 2^	Week 4^^^	Week 6^	Week 8^^^	Week 10^	Week 12^^^	Week 16^^^
Parent Ratings [1]									
Demographics	X								
SCID-5 [2]	X								
MADRS [3]	X	X		X		X		X	X
HAM-D [4] (optional)		X		X		X		X	X
GDS-CS [5]		X		X		X		X	X
PSQI [6]		X							X
Subject Assessments									
Vital Signs, Height, Weight (optional for remote visits)	X								X
Urine Pregnancy Test [7]	X								
Pregnancy Assessment				X		X		X	X
MADRS**	X	X		X		X		X	X
HAM-D** (optional)		X		X		X		X	X
GDS-LD**		X		X		X		X	X
Stanford-Binet-5 (SB-5) or other cognitive assessment	X								
Treating Clinician									
DS Diagnosis [8]	X								
Diagnostic Exam including medical/psychiatric history	X								
Health/Behavior Review	X								
Adverse Effects Review		X	X	X	X	X	X	X	X
CGI-Severity [9]	X	X							X
CGI-Improvement [10]				X		X		X	X
Suicide Assessment [11] / C-SSRS [12]	X	X	X	X	X	X	X	X	X
Concomitant Treatments	X	X	X	X	X	X	X	X	X
Concomitant Medications	X	X	X	X	X	X	X	X	X

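### No pregnancy test or question is scheduled at Baseline, where fluoxetine is prescribed, and no limit is set on the age of the Screen test

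*Combined protocol and SAP*

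**What the plan says.** Exclusion criterion 3 (Section 4) bars pregnancy and also sexual activity without acceptable contraception. Section 7, on risks to an embryo or fetus, says that the drug passes the placenta and may harm the fetus, and requires agreement to use birth control.

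The checks are set out in Section 6, Safety Monitoring, and in Table 1:

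- **Test:** "If a participant is of childbearing potential, a urine pregnancy test will be obtained at Screen". Section 7 also places the test at Screen. Table 1 has a single mark for it, in the Screen column.
- **Questions:** "We will continue to assess for pregnancy at all monthly clinic visits". These cover sexual activity and contraception. A repeat urine test follows only when a participant reports activity without an approved method. In Table 1 the row "Pregnancy Assessment" is marked at weeks 4, 8, 12 and 16.
- **Prescription:** Section 3 states "The prescription of fluoxetine will occur at the time of the baseline visit".

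Section 3 describes Screen and Baseline as separate contacts: "Participants will be seen at screen, baseline, and following 4, 8, 12, and 16 weeks of treatment". Section 6 and the Table 1 footnotes allow them to be combined when eligibility is clear. The footnotes also allow Baseline to take place in clinic, by Zoom or by telephone.

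**The concern.** A negative pregnancy test describes the participant on the day it is taken. Here that day is Screen, but the decision to expose the participant to the drug is made at Baseline. If time passes between the two, a participant of childbearing potential can conceive after a negative test and start fluoxetine with nothing in the schedule to detect it. What is at stake is fetal exposure to a drug that the protocol itself describes as potentially harmful. The response rate, the tolerability estimate and the sample size are not affected.

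**Working it through.** The plan gives no figure to reproduce. The check is a reading of Table 1 against the text, with simple counting.

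**1. Visits and pregnancy entries in Table 1**

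| Visit | Designated telephone visit | Urine test | Pregnancy Assessment |
|---|---|---|---|
| Screen | no | yes | – |
| Baseline (drug prescribed) | no | – | – |
| Week 2 | yes | – | – |
| Week 4 | no | – | yes |
| Week 6 | yes | – | – |
| Week 8 | no | – | yes |
| Week 10 | yes | – | – |
| Week 12 | no | – | yes |
| Week 16 | no | – | yes |

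- Visit columns: 9. Designated telephone visits: 3 (weeks 2, 6 and 10). Remaining visits: 9 − 3 = 6.
- Remaining visits with a pregnancy entry: 1 test + 4 assessments = 5 of 6. Baseline is the exception.

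The column positions can be trusted. The CGI-Improvement row, which can only begin on treatment, has the same pattern as the Pregnancy Assessment row, and the HAM-D row shows where the Baseline column falls.

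**2. Checks between Screen and first dose**

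- Combined visit: the Screen test is done at the prescribing visit, so the gap largely closes. Only the delay from prescription to first dose remains.
- Separate visits: 0 scheduled tests and 0 scheduled pregnancy questions after Screen and before first dose. The next entry is at week 4, after 4 weeks of treatment.

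**3. Age of the Screen test at first dose**

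Let *g* be the days from Screen to Baseline and *d* the days from prescription to first dose. The age of the test at first dose is *g* + *d*.

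- The readable text gives no value or upper limit for *g*.
- It gives none for *d* either. Section 6 has the drug supplied through the participant's insurance, with prior authorization where needed, so *d* may exceed zero.

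No age can be calculated, and none is bounded. With a validity window of *W* days applied at first dose, the age of the latest test would be at most *W*.

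**4. Other contacts at Baseline**

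- "Concomitant Medications" is reviewed. This could reveal whether a contraceptive pill is being taken, but not abstinence, condom use or pregnancy.
- The Adverse Effects Review uses a list of side effects that does not include pregnancy.
- Severity criteria are formally confirmed a second time. The MADRS threshold applies at both visits, and the CGI-S criterion is likewise worded "for depression symptoms at Screen and Baseline". The pregnancy exclusion has no such repeat.

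**The case against.** The strongest reply is that the risk is already controlled. Unprotected sexual activity is an exclusion, birth control must be agreed, and physicians see participants at Baseline and ask about doctor visits, new medication and other complaints. Section 6 also commits to monitoring for pregnancy during the whole study. These safeguards lower the risk. But the first two rely on adherence continuing after Screen, and none is a scheduled check of pregnancy status before first dose. The protocol itself asks again about contraception at every later monthly visit, so it does not treat the initial agreement as enough.

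Four narrower objections have some force:

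- **The 5 of 6 count mixes one test with four sets of questions.** This is correct. It also means that adding the questions at Baseline would not detect a pregnancy in someone who reports using contraception. The repeat test within a window does most of the work.
- **Many eligibility items are assessed at Screen only**, including the SCID-5, the DS diagnosis and the cognitive assessment, and the MADRS and CGI-S need baseline values anyway. So a Screen-only check is not unusual in this plan. Pregnancy differs from a DS diagnosis, however, because it can change between visits and bears directly on whether the drug is safe to start.
- **The 4 weeks reflects visit spacing** and would be the same if Baseline were marked. That is true. It matters here only because, with Baseline blank, week 4 is the first scheduled opportunity to notice a conception that preceded the first dose.
- **The study-design figure in Section 3 is not reproduced in the available copy** and might show an interval. That would bear on the missing limit, but not on the empty Baseline column.

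**Conclusion.** The concern holds. As written, a participant of childbearing potential with separate Screen and Baseline visits can be prescribed fluoxetine on the strength of a pregnancy test of unlimited age, with no scheduled pregnancy question at the prescribing visit. The conclusion assumes that no interval limit appears in the figure that could not be read.

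The number affected is not given and is probably small: it requires childbearing potential, separate visits and conception in between, among 25 planned participants. The potential harm is serious and preventable, and the trial's estimates do not depend on it. The change should be made because it is cheap and protects participants.

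**What to change.** 1. Add a Pregnancy Assessment mark in the Baseline column of Table 1, to be completed before prescribing whenever Baseline is not on the same day as Screen.
2. State a short validity window for the Screen urine test, measured at first dose and chosen by the sponsor. If the test will be older than that, repeat it for participants of childbearing potential, with the blood confirmation of a positive result that Section 6 already describes.
3. For a Baseline visit by Zoom or telephone, have the test done locally or at home, and do not start the drug until the result is negative.

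The document cost is one table mark and a sentence or two on the window and remote testing. The practical cost is an occasional repeat urine test and a possible short delay in starting treatment, mainly when Baseline is remote. Combining Screen and Baseline, where eligibility is clear, avoids most of it.
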